### 5.2 Endpoint Variables

The sources for the endpoint variables can be found in **Table 1**, **Table 2**, and **Table 3** in **Section 2.3.1** and **Section 2.3.2**.

### 5.3 Timing of Analyses

The Uncomplicated Technical Success / Procedural Safety endpoint will be analyzed after all Subjects eligible for the Primary Arm Uncomplicated Technical Success / Procedural Safety Eligible Population have completed a follow-up visit in the 12 month follow-up window and have been on the study for 90 days.

The Clinically Significant Reintervention endpoint will be analyzed after all Subjects eligible for the Primary Arm Clinically Significant Reintervention Eligible Population have completed a follow-up visit in the 12 month window.

The primary safety endpoint will be analyzed in the Primary Study arm during the effectiveness analysis.

The Primary and Secondary Study arms will be treated independently from each other, with the secondary study arm limited to descriptive analysis.

The Sponsor will collect data that comprise the secondary endpoints throughout all study follow-up (5 years), as appropriate, in addition to their specified analysis times (see **Section 4.2**). For endpoint events that rely on CEC adjudication, site reported data will be used to assess endpoints after the 12 month analysis period.

Following accrual of the initial 102 study subjects into the Core Clinical Investigation, up to 65 additional study subjects will be enrolled and implanted to allow for Continued Access to the device after the original enrollment is complete. The initial and additional subjects will be evaluated per the Inclusion / Exclusion criteria and will employ the same follow-up schedule. All statistical inference for the PMA submission will be based on the initial 102 subjects. Data from subjects enrolled in the Continued Access cohort will be reported separately but may be pooled with the initial data for subsequent follow-up reports.

Analyses of the reduced profile VBX Device will be completed once a minimum of 10 subjects (of the Continued Access phase) are enrolled and implanted with reduced profile VBX Device and followed through 30 days

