## 2. Study Design Overview

This will be a prospective, non-randomized, two-armed, multicenter study conducted at up to forty-five (45) Clinical Investigative Sites (referred to as “sites” in the remainder of this document) in the United States and Europe. A minimum of 122 subjects, up to a potential maximum of 202 subjects, will be implanted with the TAMBE Device across two independent study arms as described below.

- Primary Study Arm – Hypothesis-driven analysis, Thoracoabdominal aneurysms (TAAAs) which are anatomically suitable for treatment with the TAMBE Device and do not require proximal extension with a CTAG Device (N=102). This arm will be limited to pararenal aortic aneurysm and adapted Crawford Type IV TAAAs.
- Secondary Study Arm – Non hypothesis-driven analysis, TAAAs which are anatomically suitable for treatment with the TAMBE Device and would require proximal extension with CTAG Device(s). This arm will include adapted Crawford Type I-III TAAAs. (N=20-100 Subjects)

Up to 65 additional subjects may be implanted in the Continued Access Phase under the Primary Study Arm only. All sites will be allowed to enroll in the Continued Access Phase, and all sites and subjects will be treated and followed in the same manner as the Core Clinical Investigation.

- The reduced profile VBX Device cohort (a subset of the Continued Access phase) will follow the TAMBE protocol: all primary, secondary, and other endpoints will be collected for these subjects as per protocol in the same manner as for the other cohorts. The Target Vessel Technical Success of the reduced profile VBX Device for each vessel will also be assessed.
- To assess the compatibility of reduced profile VBX Device as a side branch component in conjunction with the TAMBE Aortic Component (AC), the following endpoints will be summarized at a subject level:
  - Uncomplicated Technical Success at Index Procedure
  - Procedural Safety data through 30-day follow-up
  - Summary of AEs through 30-day follow-up including Type Ic and IIc Endoleaks

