Lesion-related mortality	Defined as all deaths during hospitalization for index endovascular procedure and within 30 days of the index endovascular procedure or any secondary procedures due to the treated pathology, or the effectiveness of the endovascular repair (e.g., procedures to treat retrograde dissections, losses of patency, losses of device integrity, endoleaks, migrations, aortic expansions, aortic ruptures) and any deaths related to the treated pathology or endovascular graft (e.g., aneurysm rupture, retrograde dissection leading to fatal cardiac tamponade), unless evidence is available to demonstrate that the death is not lesion related	30 days or in-hospital for index endovascular procedures	
Permanent paraplegia	Paraplegia secondary to spinal cord ischemia identified within 30 days of the index endovascular procedure combined with spinal cord ischemia scale grade of "3" at the one-month follow-up visit. The grading system for spinal cord ischemia is described in TEVAR reporting standards	Event reported within 30 days of endovascular procedure without resolution at one month follow-up	
Permanent paraparesis	Paraparesis secondary to spinal cord ischemia identified within 30 days of the index endovascular procedure combined with spinal cord ischemia scale grade of "2" at the one-month follow-up visit. The grading system for spinal cord ischemia is described in TEVAR reporting standards	Event reported within 30 days of endovascular procedure without resolution at one month follow-up	
New onset renal failure requiring dialysis	New onset sustained renal failure identified within 30 days of the index endovascular procedure, combined with need/requirement for dialysis at the one month follow-up visit	Event reported within 30 days of endovascular procedure without resolution at one month follow-up	
Severe bowel ischemia	Bowel ischemia resulting in bowel resection or fatal outcome	30 days	
Disabling stroke	Stroke was assessed using the Modified Rankin Scale. Stroke identified as having occurred within 30 days of the index endovascular procedure, combined with mRS $\geq 2$ with an increase from baseline of at least one grade at 90 days  Modified Rankin Score was completed by an allied health staff member who successfully completed mRS certification or licensed medical professional	120 days (30 days for Stroke Events, plus 90 days for mRS measurements)	

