4.1 Study Collection Intervals

Subjects will be asked to return for follow-up visits at one (1), three (3), six (6), 12, 24, 36, 48, and 60 months post-treatment. At each follow-up visit, subjects will undergo an evaluation for adverse events.

Table 4: Schedule of Events

	Pre-treatment (Screening)	Treatment	Hospital Discharge	One Month	Three Months	Six Months	Annually through 5 Years
Informed Consent	X						
Demographics and Medical History	X						
Risk Scales (ASA, NYHA, SVS)	X						
Physical examination	X		X	X	X	X	X
Adverse Events	X	X	X	X	X	X	X
Medication Review	X		X	X	X	X	X
Modified Rankin Scale a,b	X		X	X	X if applicable	X	
Spinal Cord Ischemia Scale a	X		X	X		X	

NIH Stroke Scale c	X		X If applicable				
SF-36 Questionnaire	X			X	X	X	X
Serum Creatinine Concentration	X		X	X	X	X	X
Spiral CTA (contrast) d	X			X		X	X
Spiral CT (non-contrast)				X		X Optional	X Optional
Completion Angiogram		X					
Magnified Branch Visualization		X					
Abdominal Ultrasound	X		X	X	X	X	X
Multiplanar Device Radiographs (X Ray)				X		X	X

a If subject is unable to return to the site for a follow-up visit, they may be contacted by telephone to evaluate the Modified Rankin Scale and Spinal Cord Ischemia Scale.

b For subjects suspected of having a stroke event within 30 days following the index endovascular procedure an additional mRS score should be completed at 90 days following the suspected stroke event but no greater than 120 days post index endovascular procedure.

c NIH Stroke Scale should be performed for any subject suspected of having a stroke event that undergoes the treating site's stroke protocol during the study interval from the initiation of the index endovascular procedure until discharge. The scale should be performed as soon as possible after learning of the suspected event and again at the time of discharge.

d CTA of chest/abdomen/pelvis at Screening. CTA of abdomen and pelvis at all follow-up visits, except for Secondary Study Arm Subjects who must have a CTA of chest/abdomen/pelvis at all visits. MRA may be used in place of CTA during follow-up if the Subject is contraindicated for CTA.

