#### 5.4 Statistical Analysis of Endpoints

One-sided exact Clopper-Pearson confidence intervals for binomial proportions ( $\alpha=0.05$ ) will be constructed to test the Uncomplicated Technical Success and Clinically Significant Reintervention hypotheses in the Primary Study Arm. The null hypothesis for each endpoint will be rejected if the lower bounds of the 95% confidence interval exceeds the corresponding performance goal. This is equivalent to stating that the estimated effectiveness and safety must exceed the PG with a Type I error rate ( $\alpha$ ) of  $< 0.05$ .

Primary and Secondary Endpoints will be summarized in the Secondary Study Arm, but no hypotheses tests will be performed.

All events must meet the protocol definition.

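### The reduced profile VBX summary may be completed at 30 days, before a recent non-fatal stroke has the 90-day mRS that its safety composite requires

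*Combined protocol and SAP*

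**What the plan says.** SAP Section 5.3 states that the reduced profile VBX analyses "will be completed once a minimum of 10 subjects (of the Continued Access phase") have been "enrolled and implanted with reduced profile VBX Device and followed through 30 days". Section 2 lists what they summarize at subject level: technical success at the index procedure, "Procedural Safety data through 30-day follow-up", and adverse events over the same period. Section 2 also keeps this cohort on the common endpoints: "all primary, secondary, and other endpoints will be collected for these subjects as per protocol in the same manner as for the other cohorts".

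Procedural Safety is defined in Table 1 and has seven elements. For disabling stroke, the stroke must occur within 30 days of the index procedure, and the mRS must be at least 2, "with an increase from baseline of at least one grade at 90 days". The evaluation time is given as "120 days (30 days for Stroke Events, plus 90 days for mRS measurements"). Table 4, footnote b, agrees: for a suspected stroke within 30 days, "an additional mRS score should be completed at 90 days following the suspected stroke event but no greater than 120 days post index endovascular procedure".

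Section 5.4 adds the counting rule: "All events must meet the protocol definition". Section 5.4.1 counts as events only those that meet the Section 2.3.1 definition.

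**The concern.** The VBX analysis may be completed at a point when one element of its safety composite cannot yet be decided for recently treated subjects. A non-fatal stroke in such a subject neither meets nor fails the definition, because the deciding mRS has not been taken. Under the counting rule it does not enter the composite as an event. The readable text has no pending category and no 30-day version of the stroke element. The VBX population in Section 5.1 requires only implantation of at least one such device, so it adds no follow-up condition.

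The error can run in one direction only, towards fewer events. In a group that may be as small as 10, one subject is 10 percentage points. The same endpoint in the Primary Study Arm does not have this problem, because Section 5.3 makes that analysis wait for the 12-month visit and 90 days on study.

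**Working it through.** **Inputs from the documents**
- VBX trigger: at least 10 subjects, 30 days (Section 5.3).
- Stroke eligible from day 0 to day 30; mRS 90 days after the stroke; latest day 120 (Table 1; Table 4, footnote b).
- One-month visit: ideal window days 23-44, analysis window days 15-59 (Table 5).
- 12-month analysis window opens on day 243 (Table 5).
- Planned Primary Study Arm accrual: 102 subjects in 27 to 32 months (Section 2.6).

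**1. The plan's own figure.** 30 + 90 = 120 days, which matches Table 1 and footnote b.

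**2. Shortfall at the trigger.** A stroke on day s can be scored from day s + 90. For a subject at day 30 the shortfall is (s + 90) - 30 = s + 60 days.
- s = 0: scorable from day 90, 60 days short.
- s = 30: scorable from day 120, 90 days short.

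The subject who sets the trigger by reaching day 30 is therefore always 60 to 90 days short.

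**3. Comparison with the Primary Study Arm.** The earliest day in the 12-month analysis window is 243, which is later than day 120. Every stroke within 30 days is past its scoring date when that analysis is run.

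**4. How many of the first 10 subjects are affected.** If subjects arrive every g days, subject k has 30 + (10 - k) x g days of follow-up when subject 10 reaches day 30. The documents give no VBX accrual rate, so g is an assumption. At the planned Primary Study Arm rate, g = 27 x 30.44 / 102 = 8.1 days to 32 x 30.44 / 102 = 9.6 days.

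| Assumed gap g (days) | Subjects with at least 90 days | Subjects with at least 120 days |
|---|---|---|
| 8.1 | 2 of 10 | 0 of 10 |
| 9.6 | 3 of 10 | 0 of 10 |
| 15 | 6 of 10 | 4 of 10 |
| 30 | 8 of 10 | 7 of 10 |

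Slower accrual shrinks the problem but does not remove it.

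**5. How likely it is to matter.** The documents give no stroke rate. The chance of at least one stroke in 10 subjects is 1 - (1 - p)^10. For assumed 30-day rates p of 1%, 2%, 3% and 5% this is 10%, 18%, 26% and 40%. These figures are for any stroke. Only those non-fatal and still without the 90-day mRS are at issue, so the chance of an affected summary is lower.

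**6. The one-month elements.** Permanent paraplegia, permanent paraparesis and dialysis are judged at the one-month visit. If 30 days means literal day 30, that visit may come up to 44 - 30 = 14 days later (ideal window) or 59 - 30 = 29 days later (analysis window). If it means the completed visit, there is no gap.

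**The case against.** Much can be said for the plan as written.

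- **The stroke is not hidden.** The VBX outputs include adverse events through 30-day follow-up, where the stroke would be seen. A fatal stroke within 30 days would normally enter as lesion-related mortality. The 90-day mRS is still required and will be collected. This stands: the defect is a misclassified composite, not a lost event.
- **A reader might infer that four of the seven elements cannot be scored.** The documents do not support that. The synopsis schedule uses 30 day as the name of the one-month visit, and Table 3 uses it in the same sense for extended clinical success and aneurysm enlargement. On that reading paraplegia, paraparesis and dialysis are available at the trigger. Only the stroke element is firmly affected.
- **A reader might infer that no stroke can be scored.** Section 5.3 sets an earliest time and gives no data-cut rule. Subjects treated earlier may already have their 90-day mRS, as the table above shows.
- **The plan does not say that a pending stroke is a success.** This is correct: no readable sentence assigns such a subject to event-free, pending or missing. What follows from Sections 5.4 and 5.4.1 is narrower: the stroke is not counted as an event.
- **Interval figures might seem to show a changed result.** With 10 subjects, one-sided 95% Clopper-Pearson lower limits are 60.6% for 9/10 and 74.1% for 10/10. The plan sets no interval, hypothesis or performance goal for the VBX cohort, so no decision threshold is crossed.
- **Redaction.** Section 5.6 and much of Sections 7 and 8 are blacked out, and the clinical protocol sections cited are not in the file. Handling of pending events may be stated there.

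**Conclusion.** The point holds for one element of one summary. As Section 5.3 reads, the VBX composite can be completed when a non-fatal stroke in a recently treated subject cannot meet the Table 1 definition, and the counting rule then leaves it out. The shortfall is 60 to 90 days for a subject at day 30. The number of subjects exposed depends on accrual, which the documents do not give for this cohort.

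A reader might infer that the trial's safety conclusion is at risk. It is not: Section 5.3 bases all inference for the PMA submission on the initial 102 subjects, and the VBX cohort is a descriptive subset of Continued Access. The conclusion assumes that the redacted text holds no rule for strokes awaiting an mRS. The change is still worth making, because the misclassification runs one way and is cheap to prevent.

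**What to change.** In Section 5.3:

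1. Change the trigger to at least 10 subjects with a completed one-month visit. This also settles what 30 days means for paraplegia, paraparesis and dialysis.
2. Finalize the composite only when every VBX subject with a suspected stroke within 30 days has the 90-day mRS or has reached day 120.
3. If results are reported earlier, show such a subject as stroke, severity pending, and not as event-free. Give the composite with and without that subject as an event, and update it when the mRS is available.

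Counting every pending stroke as an event in the single reported figure is not advised. It would contradict Section 5.4 and would include strokes that later prove non-disabling.

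The cost is a few sentences. Waiting for the mRS delays the final composite by at most about 120 - 30 = 90 days, and only if a stroke is suspected. Requiring the one-month visit adds nothing if that is already the intended meaning, and at most 29 days within the analysis window if literal day 30 was meant.

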#### 5.4 Statistical Analysis of Endpoints

One-sided exact Clopper-Pearson confidence intervals for binomial proportions ( $\alpha=0.05$ ) will be constructed to test the Uncomplicated Technical Success and Clinically Significant Reintervention hypotheses in the Primary Study Arm. The null hypothesis for each endpoint will be rejected if the lower bounds of the 95% confidence interval exceeds the corresponding performance goal. This is equivalent to stating that the estimated effectiveness and safety must exceed the PG with a Type I error rate ( $\alpha$ ) of  $< 0.05$ .

Primary and Secondary Endpoints will be summarized in the Secondary Study Arm, but no hypotheses tests will be performed.

All events must meet the protocol definition.

##### 5.4.1 Uncomplicated Technical Success / Procedural Safety Endpoint Events

Uncomplicated Technical Success endpoint events in each study arm will be computed as all enrolled Subjects experiencing an event meeting the definition in **Section 2.3.1**.

##### 5.4.2 Clinically Significant Reintervention / Lesion Related Mortality Events Endpoint Events

Clinically Significant Reintervention endpoint events in each study arm will consist of all enrolled Subjects experiencing an event meeting the definition in **Section 2.3.1**.

#### 5.5 Adverse Events

The definition for Anticipated Adverse Events is given in Section 9.1 of the protocol. Section 9.1.1 describes the assessment of AE relationships, Section 9.1.2 describes determination of seriousness, and Section 9.1.3 describes their reporting and coding.

5.6

[Redacted]

5.6.1

[Redacted]

5.6.2

[Redacted]

[REDACTED]

[REDACTED]

[REDACTED]

[REDACTED]

[REDACTED]

[REDACTED]

[Redacted]

**6. Interim Analyses and Safety Monitoring Analyses (if applicable)**

Safety data will be periodically reviewed by a Data Safety and Monitoring Board (DSMB), but these reviews will not constitute statistical analyses and therefore no adjustments for multiple testing will be necessitated. A comprehensive summary of all reported adverse events will be reviewed.

**7. Analysis Specifications**

7.1 [Redacted]

- [Redacted]

7.3 Verification Level for Statistical Output

All necessary analysis datasets as well as tables referenced herein will be verified at Level I. All listings referenced herein will be verified at Level II. Verification levels are explained in MD111325 Clinical Affairs Biostatistics Analysis Specification and Programming.

[Redacted]

## 8. Data Sets, Tables, Figures, and Listings

This section includes a list of the minimal planned statistical outputs, including tables, listings and figures which are to be created for the regulatory reports defined in the protocol. A different selection of tables, listings, and figures can be created for all other reporting efforts (DSMB, Annual Report, etc.) as decided necessary. Dataset names and descriptions may also be included.

### 8.1

[REDACTED]

- [REDACTED]
- i [REDACTED]

[REDACTED]

[REDACTED]

[REDACTED]

9. [REDACTED]

[REDACTED]

[REDACTED]

[REDACTED]

[REDACTED]

[REDACTED]

[REDACTED]

[REDACTED]

[REDACTED]	[REDACTED]	[REDACTED]
[REDACTED]	[REDACTED]	[REDACTED]
[REDACTED]	[REDACTED]	[REDACTED]
